In Part B of the study, subjects in the decitabine plus talacotuzumab arm will receive talacotuzumab IV at the RP2D over approximately 180 minutes. Talacotuzumab will be administered on Days 8 and 22. Decitabine will be administered at 20 mg/m² as a 1-hour IV infusion for 5 consecutive days (Days 1 to 5) every 28 days (1 treatment cycle) to subjects in both treatment arms. During the first 4 treatment cycles, all subjects in the decitabine + talacotuzumab arm must receive premedication with dexamethasone, methylprednisolone, acetaminophen (paracetamol), cimetidine, diphenhydramine, and montelukast prior to talacotuzumab dosing to prevent infusion-related reactions. If no infusion-related reactions are seen for

2 consecutive cycles during the first 4 cycles, then premedication may be modified by the investigator after discussion with the Sponsor for Cycle 5 and subsequent talacotuzumab treatments. In the event an infusion-related reaction (independent of severity) occurs in Cycle 5 and subsequent talacotuzumab treatments, premedications need to be reintroduced.

Subjects in the decitabine only arm will receive the 5-Day decitabine dosing regimen (20 mg/m² as a 1-hour IV infusion for 5 consecutive days every 28 days) alone.

EFFICACY EVALUATIONS

Disease evaluations will include peripheral blood assessments, bone marrow assessments, and clinical presentation. Disease status will be evaluated according to Response Criteria in AML with modifications for treatment failure. Survival status and subsequent anticancer therapy will also be collected. Blood samples will also be collected to assess pharmacokinetics, immunogenicity, pharmacodynamics, MRD, and biomarkers.

Following Amendment 6, which incorporated the IDMC's recommendations to close enrollment to the study and discontinue talacotuzumab treatment for subjects receiving talacotuzumab + decitabine and offer to continue decitabine alone, all subjects will continue to be followed for survival and subsequent anti-cancer therapy. During the treatment phase with decitabine, subjects will be monitored for serious adverse events.

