6.1.2. Part B

In Part B of the study, subjects will receive study therapy according to the arm to which they are assigned. The start of each cycle is defined as the date of the first dose of decitabine. Cycles may be delayed due to recovery from toxicity or other causes. Study treatment continues until treatment failure, relapse from CR/CRi, unacceptable toxicity, death, or other reasons specified in Section 10.2.

In Arm 1, study therapy Cycle 1 will start with decitabine at a dose of 20 mg/m² IV administered daily for five consecutive days followed by IV treatment with talacotuzumab (at the RP2D) on Days 8 and 22 (\pm 24 hours) of a 28-day cycle. Subsequent cycles of study therapy will follow the same dosing schedule as Cycle 1 as outlined in Table 3.

Table 3: Dosing Schedule for Part B - Arm 1

Study Day	All treatment cycles									
	1	2	3	4	5	6-7	8	9-21	22	23-28
Decitabine (20 mg/m ²)	X	X	X	X	X					
Talacotuzumab (RP2D mg/kg)							X		X	

Subjects assigned to Arm 2 will receive decitabine at a dose of 20 mg/m² IV administered daily for five consecutive days. A Cycle of study therapy will be repeated every 28 days from the first dose of decitabine onwards. The dosing schedule for Arm 2 is outlined in Table 4.

Table 4: Dosing Schedule for Part B - Arm 2

Study Day	All treatment cycles					
	1	2	3	4	5	6-28
Decitabine (20 mg/m ²)	X	X	X	X	X	

Investigators should be aware that for treatment with decitabine as monotherapy or in combination, it is recommended that subjects be treated for a minimum of 4 cycles; however, a complete or partial response may take longer than 4 cycles.

Study treatment is to continue until treatment failure, relapse from CR/CRi, or death, unless discontinued early because of unacceptable toxicity. Subjects in Arm 1 may discontinue 1 of the study treatments (decitabine or talacotuzumab) because of unacceptable toxicity and continue treatment the other agent until treatment failure, relapse from CR/CRi, or death, unless discontinued early because of unacceptable toxicity.

Following Amendment 6, enrollment to the study was closed and subjects receiving talacotuzumab + decitabine should discontinue talacotuzumab treatment and may continue to receive decitabine alone, according to Principal Investigator decision and subject agreement.

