12.3.1. All Adverse Events

All adverse events and special reporting situations, whether serious or non-serious, will be reported from the time a signed and dated ICF is obtained until 30 days following the last dose of study drug. During the Follow-up Phase, adverse events of Grade 3 or higher that are considered related to study drug, as well as all related serious adverse events, should be followed until resolution.

Serious adverse events, including those spontaneously reported to the investigator within 30 days after the last dose of study drug, must be reported using the Serious Adverse Event Form. The sponsor will evaluate any safety information that is spontaneously reported by an investigator beyond the time frame specified in the protocol. Anticipated events will be recorded and reported as described in [Attachment 4](#).

Treatment failure or relapse from CR/CRi should not be recorded as an adverse event or serious adverse event term; instead, signs and symptoms resulting from disease relapse/lack of efficacy will be reported if they fulfill the serious adverse event definition (refer to Section 12.1.1 Adverse Event Definitions and Classifications). Death should not be recorded as an adverse event or serious adverse event, but as the outcome of an adverse event. The adverse event that resulted in the death should be reported as a serious adverse event. All events that meet the definition of a serious adverse event will be reported as serious adverse events, regardless of whether they are protocol-specific assessments.

All adverse events, regardless of seriousness, severity, or presumed relationship to study drug, must be recorded using medical terminology in the source document and the eCRF. Whenever possible, diagnoses should be given when signs and symptoms are due to a common etiology (eg, cough, runny nose, sneezing, sore throat, and head congestion should be reported as "upper respiratory infection"). Investigators must record in the eCRF their opinion concerning the relationship of the adverse event to study therapy. All measures required for adverse event management must be recorded in the source document and reported according to sponsor instructions.

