5.15. Treatment-Emergent Adverse Events

Treatment-emergent AEs are defined as those that occurred after the first dose of study drug through the last dose date + 30 days or the start of a subsequent anticancer therapy, whichever occurs earlier. Adverse events that occurred any time after the first dose of study drug during the study are also considered as treatment-emergent if they are study drug-related (ie, possible, probable, or very likely related to study drug).

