6.8. Safety

6.8.1. Adverse Events

Adverse events are coded to SOC and PT terms using the Medical Dictionary for Regulatory Activities (MedDRA) coding system version 18.0 or higher.

Severity of AEs will be graded on a scale of 1 to 5 according to the NCI Common Terminology Criteria for Adverse Events (NCI CTCAE version 4.0 or higher). Adverse events will be summarized by grade according to the worst grade experienced.

Adverse events will be categorized and summarized according to their highest (worst) relationship to study medication.

Summaries of treatment-emergent AEs will be provided as incidence tables (number of subjects experiencing an event) by treatment group, by SOC and PT, by NCI toxicity grade, by relationship to study drug, and by action taken. Tables will be sorted by frequency in incidence (the highest to lowest incidence). The same summary will be provided for serious AEs, drug-related serious AEs, AEs leading to treatment discontinuation, and AEs leading to death.

For adverse events that are identified as special interest per Section 6.17, terms selected from standardized MedDRA queries (SMQs) and/or customized AE groupings that represent the clinical syndrome will be summarized. AEs of special interest, including infusion-related reactions, will be summarized by toxicity grade.

The number and percent of subjects who die during the study and cause of death will be summarized by treatment arm.

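### Adverse-event capture ends 30 days after the last dose, so combination-arm subjects can be observed up to 17 days longer than controls, and no exposure-adjusted AE rate is planned

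*SAP*

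**What the plan says.** SAP 5.15 sets the window: "Treatment-emergent AEs are defined as those that occurred after the first dose of study drug through the last dose date + 30 days". The sentence goes on "or the start of a subsequent anticancer therapy, whichever occurs earlier". A second rule follows: "Adverse events that occurred any time after the first dose of study drug during the study are also considered as treatment-emergent if" they are judged possibly, probably or very likely related to study drug. Both rules apply to both arms.

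Data capture has the same end point. Protocol 12.3.1 states that AEs "will be reported from the time a signed and dated ICF is obtained until 30 days following the last dose of study drug", and the AE row of Time and Events Table 1B ties the 30 days to the last dose of whichever study drug is given last.

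The two schedules end at different points of the 28-day cycle. In Arm 1, Protocol 6.1.2 has decitabine "followed by IV treatment with talacotuzumab (at the RP2D) on Days 8 and 22". Decitabine is given "for 5 consecutive days (Days 1 to 5) every 28 days (1 treatment cycle) to subjects in both treatment arms" (Protocol Synopsis, Dosage and Administration), so Day 5 is the last scheduled dose of a control cycle.

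For reporting, SAP 6.8.1 says: "Summaries of treatment-emergent AEs will be provided as incidence tables (number of subjects experiencing an event) by treatment group". It plans the same summary for serious AEs, AEs leading to discontinuation and AEs leading to death. SAP 6.7.3 defines an exposure-adjusted rate per patient-month for transfusions. There is no counterpart for AEs.

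**The concern.** A crude percentage compares two arms fairly only if subjects are watched for similar lengths of time. Here the length depends partly on the dosing calendar of the added drug. Suppose two subjects start the same last cycle, take neither a Day 8-only course nor new therapy, and both have a pneumonia on Day 40 that is judged unrelated. If the combination subject received the Day 22 dose, the event is treatment-emergent. In the control subject it falls after Day 35, outside both routine collection and the table.

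Safety is a secondary endpoint of an open-label comparison (SAP 2.2; Protocol 5). Part of any excess of AEs or SAEs in the combination arm could reflect longer observation rather than more toxicity. The extra days also come just after treatment stops, when event rates in this disease may rise.

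**Working it through.** The documents give no window length by arm and no AE rate, so there is no stated figure to reproduce. The inputs are the 30-day rule (SAP 5.15), last-dose days 22, 8 and 5 and the 28-day cycle (Protocol 6.1.2), and 30.4375 days per month (SAP 5.4).

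**1. Close of the window in the last cycle** = last-dose day + 30.
- Last dose Day 22: 22 + 30 = Day 52
- Last dose Day 8: 8 + 30 = Day 38
- Last dose Day 5 (decitabine): 5 + 30 = Day 35

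The gap to control is 17, 3 or 0 days. It arises once per subject: in every earlier cycle the 30 days run past Day 28 in both arms, so observation is continuous.

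**2. Window length for k cycles** = 28(k − 1) + 52 for a Day 22 ending, and 28(k − 1) + 35 for a Day 5 ending.

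| Cycles | Day 22 ending | Control | Ratio |
|---|---|---|---|
| 1 | 52 | 35 | 1.49 |
| 2 | 80 | 63 | 1.27 |
| 4 | 136 | 119 | 1.14 |
| 6 | 192 | 175 | 1.10 |
| 12 | 360 | 343 | 1.05 |

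**3. Effect on crude incidence when the true hazard is the same.** Assumptions: hazard 0.10 per month in both arms; number of cycles K geometric with median m, P(K = k) = (1 − q)q^(k−1), q = 0.5^(1/m); same distribution in both arms. Incidence = Σ P(K = k)[1 − exp(−0.10 × T_k / 30.4375)], with T_k from step 2. The variants act only after Day 28 of the last cycle. That tail lasts L = 52 − 28 = 24 days or 35 − 28 = 7 days. With daily event rate λ and daily truncation rate τ, the chance of an event in the tail is [λ/(λ+τ)][1 − exp(−(λ+τ)L)].

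| Scenario | Median 2 cycles | Median 4 cycles |
|---|---|---|
| All Arm 1 end on Day 22 | 30.5% vs 26.5%, ratio 1.15 | 42.4% vs 39.1%, ratio 1.08 |
| Half end on Day 22, half on Day 5 | ratio 1.08 | ratio 1.04 |
| All Day 22, truncation 0.25/month | ratio 1.13 | ratio 1.07 |
| All Day 22, hazard doubled in tail | ratio 1.27 | ratio 1.16 |
| All Day 22, doubled tail and truncation | ratio 1.24 | ratio 1.14 |

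For common events the ratio shrinks: at 1.0 per month it is about 1.06 and 1.04.

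**4. Unequal cycles.** The offset is 17/28 = 0.61 of a cycle. Three combination cycles ending on Day 22 give 56 + 52 = 108 days; four control cycles give 84 + 35 = 119 days. At 0.10 per month, incidence is 1 − exp(−0.10 × 108/30.4375) = 29.9% against 1 − exp(−0.10 × 119/30.4375) = 32.4%, ratio 0.92. The direction reverses.

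**The case against.** The strongest reply is that both arms get the same 30 days after last exposure, which is a standard, regimen-based definition, and that the SAP already summarises treatment duration and cycles by arm (SAP 6.6). That is fair as a defence of the window. It does not make the crude percentages comparable.

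A reader might infer that the whole combination arm is observed to Day 52 and that the crude tables are therefore biased against the combination. The documents do not support this:

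- Day 52 is the latest scheduled case. A talacotuzumab dose delayed by more than 3 days is skipped and not made up (Protocol 6.3.3). Arm 1 subjects may stop talacotuzumab and continue decitabine, and under Amendment 6 all of them stopped talacotuzumab (Protocol 6.1.2). Those whose last dose is Day 5 decitabine have no gap.
- Subsequent anticancer therapy or death can close the window before Day 52.
- Related events count at any time in both arms, so the artefact mainly concerns events judged unrelated. This offset may be incomplete, because routine collection itself stops at 30 days.
- One fewer combination cycle outweighs the 17 days.

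A reader might also infer that a harmless add-on would look more lethal. SAP 6.8.1 separately summarises all deaths during the study with cause, without the 30-day limit, so mortality can be compared free of this artefact. Nor does the recorded benefit/risk judgement rest on total AE counts: it cites lack of efficacy, infusion-related reactions and premedication complexity (Protocol 3.1).

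All of this limits the size and the certainty of direction. It does not remove the difference in observation time or supply an adjusted analysis.

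**Conclusion.** The point holds in a limited form. Following the plan as written, a combination subject who ends on a Day 22 dose has up to 17 more days of AE capture than a control subject, once, and AEs are then reported with no time denominator. At equal cycles and equal hazards this inflates crude incidence in the combination arm, mainly for AEs judged unrelated.

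The size is modest. At an assumed 0.10 per month, the ratio is about 1.04 to 1.15 across the constant-hazard scenarios. The larger ratios, 1.14 to 1.27, all need a hazard that doubles after Day 28 of the last cycle; truncation alone does not produce them. The hazard, the cycle distribution, the truncation rate and the share ending on Day 22 are assumptions. The net direction across the trial cannot be stated without the cycles received in each arm. A supportive analysis should be added; the planned tables need not be replaced.

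**What to change.** In SAP 6.8.1, keep the crude tables and add the following.

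1. **Exposure-adjusted incidence rates** for treatment-emergent AEs, Grade 3 or higher AEs, SAEs and AEs leading to death: subjects with a first event per patient-month, from first dose to first event or, if none, to the earliest of last dose + 30 days, subsequent anticancer therapy, death and clinical cutoff. Count only events inside that window. Otherwise the any-time rule for drug-related AEs puts events in the numerator that have no matching time in the denominator.
2. **For non-serious AEs**, also end the window when their collection stopped under Amendment 6, after which only serious AEs were monitored (Protocol 12.3, Time and Events Table 1C).
3. **A supportive table cut in both arms at last decitabine dose + 30 days**, the same point of the cycle in each arm. This is needed because a person-time rate does not remove the bias if the event rate rises after treatment stops. It does not correct for differences in cycles received; the rates in item 1 address those if the event rate is roughly constant.

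The cost is a paragraph of SAP text and a few tables from data already collected. The decitabine-anchored table leaves out late Arm 1 events, including any in subjects who continued talacotuzumab alone, so it should be labelled supportive only.

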5.16. Adverse Events of Special Interest

Adverse events of special interest are defined as the following:

- Infusion-related reactions
- Development of anti-drug antibodies (ADA)
- Bleeding, with or without thrombocytopenia
- Thrombotic events, including myocardial infarction (MI), cerebrovascular accident (CVA), and pulmonary embolism (PE)
- Infections by severity and seriousness criteria, with and without neutropenia

- Febrile neutropenia

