2. OBJECTIVES, ENDPOINTS, AND HYPOTHESIS

2.1. Objectives and Endpoints

2.1.1. Objectives

Primary Objectives

Part A: to assess the safety of talacotuzumab monotherapy and confirm the RP2D in subjects with AML for whom experimental therapy is appropriate (as assessed by their treating physician).

Part B: The primary objectives of the study are to assess CR rate and OS in subjects with previously untreated AML who are not eligible for intense induction chemotherapy and who are randomly assigned to receive decitabine plus talacotuzumab at the RP2D or decitabine alone.

Secondary Objectives (Part B)

The secondary objectives are:

- To assess EFS;
- To determine the overall response rate (ORR) defined as rate of complete response (CR) and complete response with incomplete blood count recovery (CRi);
- To determine the rate of CR plus MRD negative CRi
- To assess the relapse-free survival (RFS);
- To assess time to response and duration of response for subjects who achieve CR/CRi;
- To assess minimal residual disease (MRD);
- To assess the safety profile of talacotuzumab in combination with decitabine;
- To assess the pharmacokinetics of talacotuzumab and decitabine alone and in combination;
- To assess the immunogenicity talacotuzumab alone (Part A) and in combination with decitabine (Part B);
- To assess patient-reported outcomes (PROs) using the FACT-Leu and EQ-5D-5L.

Exploratory Objectives

The exploratory objectives are:

- To explore PK/PD relationships of talacotuzumab through analysis of talacotuzumab PK, biomarkers, PD markers, and clinical end points;
- To explore biomarkers predictive of clinical response;
- To collect medical resource utilization (MRU) data that may be used in future economic modeling (the construction and reporting of the economic model will be conducted separately from this study).

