9.3.4. Immunogenicity Assessments

For all subjects in Part A and those randomized to receive decitabine + talacotuzumab in Part B, venous blood samples will be drawn to assess the generation of antibodies to talacotuzumab (immunogenicity), as specified in the [Time and Events Schedule Tables 2A](#) and [2B](#). Additionally, blood samples to assess immunogenicity should be collected at the final visit for subjects who discontinue treatment or withdrawn from the study. Subjects who discontinue treatment in Part B will also be asked to return for an immunogenicity evaluation during the Follow-up Phase.

All samples collected for immunogenicity analysis will be evaluated for talacotuzumab serum concentration to ensure appropriate interpretation of immunogenicity data. At each time point, immunogenicity and serum talacotuzumab concentration analyses will be performed on aliquots from the same blood draw and no additional sampling is required. Procedures for sample collection, preparation, identification, storage, and shipment will be provided in the Laboratory Manual or equivalent document.

Serum samples will be screened for antibodies binding to talacotuzumab and serum titer will also be determined from confirmed positive samples using validated assay methods by or under the supervision of the sponsor. Other immunogenicity analyses (eg, assessment of neutralizing capabilities) may be performed to further characterize the immune responses that are generated.

Any time an infusion-related reaction is observed or reported during the study, a blood sample should be drawn for determination of antibodies to talacotuzumab. Talacotuzumab serum concentration will also be determined from the same infusion-related reaction sample for the purpose of interpreting immunogenicity data. These samples will be stored and evaluated if deemed necessary. If the infusion-related reaction results in treatment discontinuation, then subjects should undergo all scheduled safety and efficacy evaluations. Samples collected for the analysis of talacotuzumab immunogenicity/serum concentration may additionally be used to evaluate safety or efficacy aspects that address concerns arising during or after the study period or for the evaluation of relevant biomarkers by the sponsor or sponsor's designee.

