11.6. Immunogenicity Analyses

The incidence of antibodies to talacotuzumab (immunogenicity) will be summarized for all subjects who receive at least 1 dose of talacotuzumab and have appropriate samples for detection of antibodies to talacotuzumab.

A listing of subjects who are positive for antibodies to talacotuzumab will be provided. The maximum titers of antibodies to talacotuzumab will be summarized for subjects who are positive for antibodies to talacotuzumab.

Other immunogenicity analyses may be performed to further characterize the immune responses that are generated.

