2.2. Secondary and Exploratory Endpoints (Part B)

Secondary endpoints to be summarized in the clinical study report include the following:

- Event-free survival (EFS), defined as the time from randomization to treatment failure, relapse from CR or CR with incomplete blood count recovery (CRi), or death from any cause, whichever occurs first. Treatment failure is defined as >25% absolute increase in the bone marrow blast count from baseline to the present assessment.
- Overall response rate (ORR, CR + CRi)
- Rate of CR plus minimal residual disease (MRD) negative CRi
- Time to response, defined for subjects who achieved a best response of CR or CRi as time from randomization to achieving the best response
- Duration of response, defined for subjects who achieved a best response of CR or CRi as time from achieving CR or CRi to relapse
- MRD negativity
- Patient-reported outcomes (PROs) using the FACT-Leu (FACT-Leu Subscale, Trial Outcome Index, Physical Function, Functional Well-being, FACT-Leu Total Score, Emotional Well-being, Social/Family Function) and EQ-5D-5L (index score and Visual Analogue Scale [VAS] score).
- Safety

Transfusion frequency will be an exploratory endpoint to be summarized in the clinical study report.

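### The SAP would count anti-drug antibodies, an assay result, from adverse-event terms, and it does not carry over the assay-based analysis in Protocol 11.6

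*SAP*

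**What the plan says.** **SAP.** Section 5.16 names "Development of anti-drug antibodies (ADA" as an adverse event of special interest. For such events Section 6.8.1 states that "terms selected from standardized MedDRA queries (SMQs) and/or customized AE groupings that represent the clinical syndrome will be summarized", with presentation by toxicity grade. It refers the reader to a Section 6.17, which does not exist; the list is in 5.16. Section 5.2 assigns all safety summaries to the safety population, meaning every randomised subject who took at least one dose of study medication. Section 5.5 sets baseline at the last value no later than the day of randomisation. Immunogenicity is missing from the Section 2.2 list introduced by "Secondary endpoints to be summarized in the clinical study report include the following", and Section 6 has no immunogenicity analysis.

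**Protocol.** A secondary objective in 2.1.1 is "To assess the immunogenicity talacotuzumab alone (Part A) and in combination with decitabine (Part B", and 2.1.2 lists immunogenicity as a Part B secondary endpoint. Section 9.3.4 says "Serum samples will be screened for antibodies binding to talacotuzumab", with titres for confirmed positives. Section 11.6 plans the analysis: "The incidence of antibodies to talacotuzumab (immunogenicity) will be summarized for all subjects who receive at least 1 dose of talacotuzumab", limited to those with appropriate samples. It adds "A listing of subjects who are positive for antibodies to talacotuzumab will be provided" and a summary of maximum titres.

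**The concern.** A positive antibody assay is a laboratory finding. It is not a clinical syndrome that term groupings would find, and no instruction in the documents tells sites to report it as an adverse event. A row built under SAP 6.8.1 therefore measures how often someone entered an ADA-related term on the adverse-event form, not how often the assay was positive.

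This matters for three reasons. Immunogenicity is a secondary endpoint, and the row in 5.16 is the only place where the SAP touches it. If both documents are followed, the report carries two ADA figures from different sources with different denominators. Infusion-related reactions also weighed in the decision to stop talacotuzumab (Protocol 3.1), and Protocol 9.3.4 asks for an antibody sample at each such reaction, so readers will look for a dependable ADA result.

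**Working it through.** The plan states no ADA rate, so there is no figure to reproduce. The check sets the two rules side by side and then sizes the gap under stated assumptions.

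| | SAP 5.16 and 6.8.1 | Protocol 9.3.4 and 11.6 |
|---|---|---|
| Numerator | Subjects with a matching adverse-event term | Subjects positive by assay |
| Denominator | Safety population (SAP 5.2) | Talacotuzumab-dosed subjects with appropriate samples |
| Scale | Toxicity grade | Incidence, listing, maximum titre |

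**1. Arms.** In Protocol Time and Events Table 2B the immunogenicity row carries the footnote restricting it to the decitabine + talacotuzumab arm. SAP 6.8.1 lays out its adverse-event incidence tables by treatment group. The sentence on events of special interest does not repeat this, but if the same layout is used, the decitabine-alone column shows a figure for subjects with no ADA sample. Protocol 11.6 avoids this, because its incidence "will be summarized for all subjects who receive at least 1 dose of talacotuzumab and have appropriate samples".

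**2. Time window.** Adverse events are collected until 30 days after the last dose (Protocol 12.3.1). Table 2B also takes an ADA sample at the first follow-up visit, and Table 1B places follow-up visits every 3 months. A positive first seen there would normally fall outside collection. SAP 5.15 would admit it only if it were recorded and judged drug-related.

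**3. Baseline.** In Part B the first scheduled ADA sample is Cycle 1 Day 8 predose (Table 2B), which is after randomisation. Under SAP 5.5 no Part B subject has a scheduled ADA baseline, so pre-existing and treatment-emergent antibodies cannot be separated. In Part A the first dose and the predose ADA sample are both on Cycle 1 Day 1 (Table 2A), so one fixed study day cannot serve both parts.

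**4. Size, as illustration.** Protocol 1.2 reports antibodies in 6 of 18 Phase 1 subjects tested: 6/18 = 33.3%, exact (Clopper-Pearson) 95% CI 13.3% to 59.0%. Let *s* be the share of assay-positive subjects who also have an ADA term recorded as an adverse event, and suppose every safety-population subject in the arm is evaluable. Then

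row = *s* × assay rate

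| *s* (assumed) | Row at an assay rate of 33.3% |
|---|---|
| 0% | 0% |
| 10% | 3.3% |
| 50% | 16.7% |
| 100% | 33.3% |

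At the planned 200 subjects per arm, the assay rate corresponds to 200 × 6/18 ≈ 67 positive subjects (27 to 118 over the interval).

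**5. Indirect evidence on *s*.** Protocol Table 1 lists Phase 1 adverse events seen in 2 or more of 27 subjects and contains no ADA term. Any single ADA term was therefore recorded in at most 1/27 = 3.7%. If the 18 tested subjects are among those 27 and all 6 positives had been recorded under one term, the row would have read 6/27 = 22.2% and appeared in the table. In Phase 1, then, assay positivity did not reach the adverse-event table as a common term. That makes an undercount likely here but does not measure it.

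**The case against.** The strongest reply is that the right analysis is already planned. Protocol 11.6 gives an assay-based incidence with a suitable denominator, a listing of positives and maximum titres, and nothing in the SAP withdraws it. The SAP is also silent on pharmacokinetics, another secondary endpoint in Protocol 2.1.2, and its endpoint list is not worded as exhaustive. The omission may simply reflect a SAP that leaves bioanalytical endpoints elsewhere. This stands, and it limits the point to the row in 5.16 and the missing link to 11.6. It does not close the gap: Protocol 11 promises specific details in the SAP, and the SAP cites no other plan for ADA. Protocol 11.5 and 11.7 to 11.9 allow separate reports for population pharmacokinetic, PK/PD, biomarker and pharmacogenomic work, whereas 11.6 makes no such provision.

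A reader might go further and infer that the reported ADA incidence will be near zero whatever the assay shows. The documents do not support that. The Protocol 11.6 figure would be unaffected. Even for the SAP row, the adverse-event definition in Protocol 12.1.1 admits abnormal laboratory results and SAP 6.8.1 allows customised groupings, so some positives could be captured. Protocol 16.2.4 says exploratory research data are not returned to investigators and names immunogenicity research, but it is not explicit that this covers the secondary-endpoint assay.

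The Phase 1 rate also needs its context. It comes from CSL362, made in a different cell line, in patients in remission. Titres were low, and there was no apparent effect on pharmacokinetics or association with adverse events.

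**Conclusion.** The point holds for the SAP's row on events of special interest. The stated rule takes an assay result from adverse-event terms, grades it for toxicity and uses the wrong population. The row would probably undercount ADA, by an amount the documents do not give. If laid out by arm, it would also show a figure for an untested control arm. It would conflict with Protocol 11.6, which the SAP neither includes nor cites. The missing ADA baseline in Part B is a separate gap and follows directly from SAP 5.5 and Table 2B.

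The 0% to 33% range rests on two assumptions: that the Phase 1 rate carries over, and a recording share that is unknown. It is illustrative only. No primary endpoint, error rate or decision rule is affected, and the consequence is limited to how a secondary safety-related endpoint is reported.

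**What to change.** - Remove ADA from the term-based summary in SAP 5.16 and 6.8.1, or keep it there with the assay named as its data source.
- Carry the Protocol 11.6 analysis into the SAP, or cite the plan that holds it: talacotuzumab-dosed subjects with appropriate samples, talacotuzumab arm only, Part A separately, with incidence, a listing of positives and maximum titres.
- Add an ADA-specific baseline: the last sample before the first talacotuzumab dose (Part B: Cycle 1 Day 8 predose; Part A: Cycle 1 Day 1 predose). Use it to report pre-existing and treatment-emergent antibodies separately.
- Correct the pointer to Section 6.17.
- Optionally, cross-tabulate ADA status with infusion-related reactions. This goes beyond Protocol 11.6, so its absence is not an error.

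The cost is SAP wording and one or two tables from samples the protocol already schedules. No new data are needed, and the incidence planned in Protocol 11.6 is unchanged.
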